9.4. RANDOMISATION

Participants who have confirmation of eligibility and written informed consent will be randomised into the trial by an authorised member of staff at the trial research site.

Participants will be randomised on a 1:1 basis between KJD (Intervention) and KR (control). Randomisation will be based on a minimisation algorithm with random component stratified by delivery unit (Section 8.2.1) and OA severity (Kellgren-Lawrence Grades 2-3 vs. Grade 4 (Appendix 1)) (17).

Since KJD is not a standard technique only some participating surgeons will have the required experience of this procedure. Additionally, some surgeons may not be in individual equipoise despite there being centre equipoise. A hybrid expertise based design (18) where surgeons are categorised into delivery units allows the trial to be feasible and pragmatic.

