9.4.2. Randomisation process

Randomisation will be performed centrally using the CTRU automated secure 24-hour randomisation service which can be accessed via the web or telephone. For web and telephone randomisation the same site code, authorisation code/site staff email address and PIN used for registration will be required to access the system. The person telephoning or accessing the web address to randomise the participant must completed the Randomisation CRF available have at the time of telephoning/accessing the web as the following information will be required:

- Site code
- Details of intended delivery unit
- Participant details, including initials and date of birth
- Confirmation of informed written consent

- Confirmation of participant's eligibility for the trial
- Confirmation of completion of TUG test and ROM
- Confirmation of completion of baseline participant questionnaires

Direct line for 24-hour randomisation: [name]

Web address for 24-hour randomisation: https://lictr.leeds.ac.uk/webrand/

Participants may only be randomised into the trial by an authorised member of staff at the trial research site, as detailed on the Authorised Personnel Log.

After trial randomisation the research site will:

- Add the unique participant ID number to all CRFs and participant consent and contact details forms.
- Return a copy of the completed consent and contact details forms to CTRU
- Book/confirm the surgery and advise the participant of the randomisation allocation and date of planned surgery. Surgery should take place within 6 weeks of the date of randomisation.
- Notify the participant's GP of their participation in the trial using the approved KARDS GP Letter.

Following randomisation, CTRU will email a Participant Randomisation Notification to the research site.

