10.3.1. Knee joint distraction

A definitive external fixator construct should be used which allows for controlled linear distraction across the knee joint of 5mm along the mechanical axis of the limb. The exact nature of the construct will depend on the equipment available at the site and surgeon preference. A list of permitted devices will be detailed in the surgical manual, and sites wishing to use devices not appearing on this list must provide CTRU with details of their preferred construct during site feasibility for prior approval. All equipment used must be CE-marked and intended to be used for distraction.

During surgery, the external fixation frame should be assembled according to this manual, with a focus on meticulous pin insertion to minimise the risk of complications. Fluoroscopy will be used to assist correct pin placement. Once the assembly is complete, 2mm of axial distraction (measured at frame) should be applied across the knee joint.

The limb should then be cleaned and a final check made for soft tissue tension around fixation elements with further skin releases made as required. Pin-sites should be dressed with an absorbent non-shedding dressing. Clips and bungs are available with various systems to keep these in place and apply gentle pressure.

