The number of complications, specifically infection, will be reported as unique events and unique patients experiencing events. Joint survival is defined as time from surgery to date of additional secondary procedure, specifically knee replacement/revision knee replacement, or date of censor at patient last follow-up. Joint survival will be estimated using the method of Kaplan and Meier and presented graphically with 12 and 24 month survival estimates and risk (hazard ratio) of additional treatment in KJD as compared to KR, in the ITT population. Global quality of life (QoL) collected as part of the EQ5D-3L may be used in a quality adjusted analysis to analyse QoL and time to secondary procedure simultaneously. Radiographic assessment of joint space width, as an indicator of intrinsic cartilage repair, over a two-year period will be reported descriptively in the KJD group.

EXPLORATORY ANALYSES

Planned exploratory descriptive subgroup analyses will be carried out by delivery unit, type of KR (partial/total), type of pin (hydroxyapatite coated/not) and baseline functioning (poor/better). Tests of heterogeneity of treatment effects across subgroups (not treatment effects within subgroups) may be appropriate.

MISSING DATA

Missing outcome data may be imputed dependent on level of missing-ness and reasons for missing-ness assessing the assumption of missing at random. Sensitivity analyses will report under different assumptions about the missing data. The impact of surgical experience is expected to be minimal; however, sensitivity analyses may be conducted to investigate any impact of surgeon experience on estimates of treatment effect (41).

INTERIM ANALYSES

Interim analyses will be conducted on an annual basis for presentation to the DMEC who will monitor primarily safety outcomes and data quality as well as the underlying assumptions of the statistical design (specifically variability on the primary outcome measure). The DMEC will also review key baseline characteristics (e.g. pain) and stratification factors to ensure balance. Analyses will be agreed and documented upfront by the independent DMEC members. No formal guidelines for stopping the trial early are in place since no formal planned interim analysis of the primary outcome measure is planned (precluded by the follow-up and recruitment timelines).

KARDS protocol v1.0_190927

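### As delivered, type of KR and type of pin each exist in one arm only, so neither can define a treatment-effect subgroup; intended KR type would need to be recorded before allocation (minor)

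*Protocol*

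**What the plan says.** Under the exploratory analyses in Protocol section 14.1, the plan labels its subgroup analyses exploratory and descriptive and states: "subgroup analyses will be carried out by delivery unit, type of KR (partial/total), type of pin (hydroxyapatite coated/not"), with baseline functioning (poor or better) as the fourth factor. The next sentence reads: "Tests of heterogeneity of treatment effects across subgroups (not treatment effects within subgroups) may be appropriate". It does not say which of the four factors could carry such a test, and it excludes none.

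Other sections show where two of these factors arise:

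- **Pins** belong to the external fixator used in KJD. Section 10.3.1 says "the external fixation frame should be assembled according to this manual, with a focus on meticulous pin insertion", and on the choice of device: "The exact nature of the construct will depend on the equipment available at the site and surgeon preference".
- **KR type** is a feature of the knee replacement operation, which section 10.3.2 leaves to local practice.

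On what is fixed before allocation, section 9.4 says: "Randomisation will be based on a minimisation algorithm with random component stratified by delivery unit (Section 8.2.1) and OA severity". The list in section 9.4.2 of what must be to hand at randomisation has one surgical item: "Details of intended delivery unit". The baseline column of the schedule in section 12.2 names no intended implant. Section 8.3 describes eligible patients as needing either a UKR or a TKR, so the distinction is meaningful before allocation even though no section says that it is recorded then.

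**The concern.** A subgroup analysis of a treatment effect compares the two arms within each level of a factor and then asks whether those comparisons differ. Both arms must be present at every level. Delivery unit and baseline functioning meet that condition. Pin type and KR type, taken as delivered, do not: a KR participant has no pin type and a KJD participant has no implant type.

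Whether KJD compares differently with partial and with total replacement is a natural question for readers of this trial. If the analyst tries to answer it from the implant received, the only available comparison is UKR recipients, or TKR recipients, against everyone in the KJD arm. Each KR subset has been selected by whatever led to that implant, and the KJD arm has not been selected in that way. Randomisation does not protect the comparison. For pin type, the choice of construct follows site equipment and surgeon preference, so differences between coated and uncoated pins are mixed with differences between sites and surgeons.

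**Working it through.** **The plan's own figures.** Section 14.1 attaches no number to the subgroup analyses. The sample size in section 14.2 is not in dispute and reproduces. With margin 8, SD 21, one-sided 2.5% and 90% power:

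n per arm = 2 × (1.960 + 1.282)² × 21² / 8² ≈ 145 (stated: 146; power at 146 is 90.2%).

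146 / 0.85 = 171.8, rounded up to 172 per arm, giving 344 in total.

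**Can the interaction be estimated?** Take the model with columns [1, arm, subgroup, arm × subgroup], arm = 1 for KJD and 0 for KR, and 172 per arm. The interaction needs rank 4. A 50:50 split was used for the check; any split other than 0% or 100% gives the same ranks.

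| Subgroup factor | What happens to the interaction column | Rank |
|---|---|---|
| Pin type (varies only where arm = 1) | identical to the subgroup column | 3 of 4 |
| KR type as delivered (varies only where arm = 0) | zero throughout | 3 of 4 |
| A factor known in both arms before allocation | distinct | 4 of 4 |

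For the first two factors the interaction is not identified. More patients would not change this.

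**What the substitute comparison would measure.** Suppose there is no treatment effect in anyone. Let p be the share of UKR patients (the same mix in both arms by randomisation), d the number of KOOS pain points by which UKR patients score higher than TKR patients whatever the treatment, and m the mean of the whole KJD arm. Then:

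- UKR recipients have mean m + (1 − p)d, so KJD minus UKR = −(1 − p)d.
- TKR recipients have mean m − pd, so KJD minus TKR = +pd.
- The apparent difference between the two effects is pd + (1 − p)d = d.

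The protocol gives neither p nor d. Over an assumed range:

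| d (assumed) | p (assumed) | KJD − UKR | KJD − TKR | Apparent difference |
|---|---|---|---|---|
| 4 | 0.2 | −3.2 | +0.8 | 4 |
| 4 | 0.3 | −2.8 | +1.2 | 4 |
| 4 | 0.5 | −2.0 | +2.0 | 4 |
| 8 | 0.2 | −6.4 | +1.6 | 8 |
| 8 | 0.3 | −5.6 | +2.4 | 8 |
| 8 | 0.5 | −4.0 | +4.0 | 8 |
| 12 | 0.2 | −9.6 | +2.4 | 12 |
| 12 | 0.3 | −8.4 | +3.6 | 12 |
| 12 | 0.5 | −6.0 | +6.0 | 12 |

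The last column simply returns d. The table shows the mechanism and does not estimate a bias.

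**With intended type recorded before allocation.** The KJD arm splits in the same way as the KR arm. KJD participants intended for UKR then also have mean m + (1 − p)d, those intended for TKR have mean m − pd, and with no treatment effect both within-type differences are 0.

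**The case against.** The strongest reply is that the plan promises very little here. The analyses are labelled exploratory and descriptive, and the heterogeneity test is only something that may be appropriate. Two of the four factors can properly carry such a test. Describing KR outcomes by implant, or KJD outcomes by pin coating, is legitimate, and the same section already describes joint space width in the KJD arm alone. Section 14.1 also says that the SAP will predefine all analyses, and the choice of factors to test is ordinary SAP content.

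Most of this stands, and it rules out several stronger readings:

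- A reader might infer that the protocol commits to testing heterogeneity on all four factors. It does not. It allows tests without saying which factors are suitable.
- A reader might infer that no valid KR-type subgroup is possible. That holds for the type as delivered. Since eligible patients need a UKR or a TKR, an intended type could be stated for everyone.
- A reader might take the list in section 9.4.2 as proof that intended type is not captured. The list also omits OA severity, which is a minimisation factor, so it is not exhaustive, and the case report forms are not shown. The protocol supports only the statement that no section provides for the field.
- A reader might quote one figure for the false interaction and set it against the margin of 8. The figure would be the assumed gap handed back, and the margin governs the primary comparison, not an exploratory description. The documents also do not say how UKR or TKR is chosen, so the presence of a gap is itself an assumption.

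What the reply does not meet is timing. A SAP can restrict the tests, but it cannot create a pre-allocation record. In single delivery units, KJD participants are operated on by surgeons authorised only for KJD (sections 8.2.1 and 10.3), so the operation need not generate a statement of the implant that would have been used. Reconstructing it later would be done with the allocation known.

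**Conclusion.** The point holds as a minor one. For pin type, and for KR type as delivered, a treatment-by-subgroup interaction is not estimable, and comparing UKR or TKR recipients with the whole KJD arm is a non-randomised contrast. Any prognostic gap between UKR and TKR patients passes in full into the apparent difference in effect. This follows from the structure of the design and needs no assumption beyond pins being used only in KJD and implants being the allocated operation only in KR. The size of any distortion cannot be given from the protocol.

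The primary analysis, the non-inferiority decision and the sample size are untouched. The reason to act despite the exploratory label is that a valid KR-type subgroup depends on information best collected before allocation.

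**What to change.** 1. Add one field to the randomisation form, completed for every participant before allocation: the KR type that would be used, UKR or TKR. Define the KR-type subgroup, and any heterogeneity test on it, by that intended type.
2. State in section 14.1 that heterogeneity tests are restricted to factors defined before randomisation in both arms.
3. Report pin type only as a description within the KJD arm, labelled non-randomised.
4. If intended KR type is not collected, report KR type only as a description within the KR arm.

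The cost is one form field and a sentence or two of text. There is a small burden on surgeons, who must name an intended implant before allocation. Intended and received types may also differ, so the analysis should say that the subgroup follows intention and should report how often the two disagree in the KR arm.

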11.1. PRIMARY OUTCOME MEASURE

The primary outcome measure is the KOOS pain score within 12-months from surgery.

The Knee Injury & Osteoarthritis Outcomes Score (KOOS) is a patient-administered questionnaire, validated for use in patients with knee OA or knee injury (20). It consists of 5 domains: Pain, other Symptoms, Function in daily living (ADL), Function in sport and recreation (Sport/Rec) and knee related Quality of life (QOL). It is recommended as the PROM of choice for assessment of patients with knee OA by the International Consortium for Health Outcomes Measurement. It typically takes 10 minutes to complete. It has been used in many RCTs comparing outcomes of knee OA treatment (21–23). For the purpose of an RCT, KOOS subscale scores are recommended to be

used as the primary outcome (24). A total KOOS score has not been validated and is not recommended.

The primary outcome measure is the KOOS pain component, given pain was indicated by the PPI group as being the most important outcome. In patients with severe knee OA, pain refractory to conservative treatment is the primary indication for a surgical intervention. Knee pain associated with OA typically continues to improve for the first 12 months after an intervention and then plateaus (25). Hence the KOOS, and other outcome measures, will be requested to 24-months post-surgery.

The previous week is the time period considered when answering the questions. Standardised answer options are given (5 Likert boxes: None, Mild, Moderate, Severe, Extreme) and each question is assigned a score from 0 to 4. A normalized score (100 indicating no symptoms and 0 indicating extreme symptoms) is calculated for each KOOS domain.

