11.2. SECONDARY OUTCOME MEASURES

1. Patient reported outcomes and quality of life outcomes

a) KOOS (At component level)

KOOS domains (except pain): other Symptoms, Function in daily living (ADL), Function in sport and recreation (Sport/Rec) and knee related Quality of life (QOL).

b) Pain VAS

The pain VAS is a unidimensional measure of pain intensity (26,27), which has been widely used in diverse adult populations, including those with rheumatic diseases (26,28–30). The pain VAS is a continuous scale comprised of a 10cm horizontal length ranging from "no pain" (score of 0) to "pain as bad as it could be" or "worst imaginable pain" (score 100 [100mm scale])

c) Oxford Knee Score (OKS)

OKS is a short, reproducible, valid PROM consisting of 12 items which provides an overall scale for assessing outcomes of knee interventions and is sensitive to clinically important changes (31–33). Each question is scored from 0 to 4 with 4 being the best outcome. This method when summed produces overall scores from 0 to 48 which reflects the severity of problems that the respondent has with their knee, with 48 being the best outcome (i.e. least symptoms). It takes approximately

5 minutes to complete the form. Whilst the applicability of the OKS to the general OA population is unclear, it is commonly used for joint replacement registries and is the outcome measure of choice of the National Joint Registry for England, Wales, Northern Ireland and the Isle of Man.

2. Objective assessment of knee function

- a) The active range of movement. Measured using a goniometer at 3, 12 and 24 months, the angles in degrees will be measured with the affected leg fully extended (extension) and fully bent (flexion), to determine the range of movement (i.e. the difference in angles between the two values, extension minus flexion). A flexion deformity will be measured as a positive value and hyperextension will be recorded as negative value.
- b) **Timed-up-and-go test**. Time in seconds for the participant to rise from a chair, walk three meters, turn around, walk back to the chair, and sit down.

3. Incidence of complications

Intra-operative complications: Complications occurring during the initial trial operative procedure will be recorded.

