Adjusted estimates of the treatment effect will be estimated from multivariable regression modelling of the KOOS pain score at 12 months. Statistical significance of non-inferiority of KJD relative to KR will be based on a 2-sided likelihood-based test with a type 1 error of 2.5% in both tails, assuming KOOS pain scores (or transformed scores if appropriate) are normally distributed and adjusted by baseline score at the time of randomisation and stratification factors (delivery unit and OA severity). If the 95% confidence interval for the absolute difference in means between KJD and KR lies entirely below or includes the non-inferiority boundary (see Section 14.2) then there would be insufficient evidence to reject the null hypothesis that KJD is inferior to KR. Conversely, if the 95% confidence interval lies entirely above the non-inferiority boundary then there would be evidence to reject the null hypothesis and conclude KJD is non-inferior to KR. Further modelling will include confounders of age and BMI, observing and addressing non-linearity through use of fractional polynomial transformation. Secondary analyses of the primary outcome measure will be considered. If non-inferiority is demonstrated and KJD appears superior to the KR, based on estimated effect and CI, statistical significance for superiority will be calculated based on an ITT analysis with similar modelling strategy. A secondary analysis of the primary outcome measure will be based on random effects multilevel modelling to account for the nested and longitudinal structure of the data over the full 24 months follow-up.

ANALYSES OF SECONDARY OUTCOME MEASURES

Analysis of PROMs (KOOS components, OKS, Pain VAS and EQ5D-3L) will focus on reporting the pre-specified dimensions of the individual questionnaires. Questionnaire responses will be combined and transformed into dimension scores, according to scoring manuals where these exist, presented graphically and longitudinally. Standardised area under the curve statistics will be compared across treatment groups as an analysis conditional on patient survival.

Range of motion and timed up and go functional assessments will be reported descriptively.

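### If effect heterogeneity by baseline functioning is tested, keep the score on its numeric scale; a poor/better split weakens the test when the effect changes gradually

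*Protocol*

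**What the plan says.** Section 14.1 of the protocol, under Exploratory analyses, states that "Planned exploratory descriptive subgroup analyses will be carried out by delivery unit", and continues with type of knee replacement, pin coating and, as the last factor, "baseline functioning (poor/better). Tests of heterogeneity of treatment effects across subgroups (not treatment effects within subgroups) may be appropriate". A test across the groups is therefore optional. The section names neither the measure of functioning nor the cut value, gives no reason for two groups, and plans no analysis on the numeric scale alongside.

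The baseline measures that could serve are all numeric:
- KOOS function domains. Section 11.1: "A normalized score (100 indicating no symptoms and 0 indicating extreme symptoms) is calculated for each KOOS domain".
- Oxford Knee Score. Section 11.2: "This method when summed produces overall scores from 0 to 48".
- Timed up and go. Section 11.2: "Time in seconds for the participant to rise from a chair".
- Range of movement in degrees (section 11.2).

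Section 12.2 schedules all of them at baseline, and section 9.4.1 requires them before randomisation. In the primary outcome modelling, age and BMI enter as further covariates, "observing and addressing non-linearity through use of fractional polynomial transformation".

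**The concern.** The other subgroup factors (delivery unit, partial or total replacement, coated or uncoated pins) are categories by nature. Baseline functioning is the only numeric one that is cut. A two-group comparison treats everyone on the same side of the cut as alike and separates patients just either side of it.

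The trial is sized for the overall non-inferiority comparison only, so any interaction test is already weak. A split weakens it further when the effect changes gradually, and makes the answer depend on where the cut falls. What is at stake is a secondary but practical question: whether the KJD-KR difference varies with how well the knee worked beforehand.

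**Working it through.** **The protocol's own figure.** Section 14.2 gives a margin of 8 points, SD 21, one-sided 2.5% and 90% power. n per arm = 2 × [(1.960 + 1.282) × 21/8]² = 144.8, so 145 by the normal approximation against the stated 146. Power at 146 is 90.2%. 146/0.85 = 171.8, so 172 per arm and 344 in total. The design reproduces, and N = 2 × 146 = 292 evaluable patients is used below. The protocol gives no figure for any interaction.

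**Assumptions not in the protocol.** The baseline score is roughly normal. The effect changes linearly with it. The test is two-sided at 5%. The residual SD is 21, with no credit for baseline adjustment. The 8, 12 and 16-point gaps are illustrative.

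**Information kept by a split.** For a linear interaction this is the squared correlation between the score and its split. For a normal score cut at proportion p it is φ(z_p)²/[p(1−p)]. At the median this is 2/π = 0.637.

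| Shape and cut | Information lost |
|---|---|
| Normal, median | 36% |
| Normal, 40/60 | 38% |
| Normal, 33/67 | 41% |
| Normal, 25/75 | 46% |
| Normal, 20/80 | 51% |
| Uniform, median | 25% |
| Beta(2,4), median | 33% |
| Beta(2,4), 25/75 | 53% |

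After a median split of a normal score, 292 patients count as 292 × 0.637 ≈ 186 for this question.

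**Power under a linear gradient.**
- Split at the median: SE of the difference in effect = 4 × 21/√292 = 4.92.
- Numeric score, per SD: SE = 2 × 21/√292 = 2.46.
- The mean scores of the two halves lie 2√(2/π) = 1.596 SD apart, so a gap g between halves means a slope of g/1.596 per SD. For g = 8 the slope is 5.01.
- For g = 8: split, 8/4.92 = 1.63, power 37%; numeric, 5.01/2.46 = 2.04, power 53%.

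| Gap between halves | Median split | Numeric, linear |
|---|---|---|
| 8 points | 37% | 53% |
| 12 points | 68% | 86% |
| 16 points | 90% | 98% |

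With the gradient that gives the 8-point gap, a 30/70 cut has 34% power and a 20/80 cut 30%.

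**Check by simulation.** A slope of 6.9 points per SD gives the numeric test 80% power and the median split 61% by formula. In 4,000 simulated trials the figures were 80% and 58%.

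**Power if the effect steps at the median.** The split keeps its 37%, 68% and 90%. The linear test's signal shrinks by √(2/π) = 0.798. For 8 points, 1.627 × 0.798 = 1.30, which gives roughly 25% power. For 12 and 16 points it is 50% and 74%.

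**Price of a flexible form.** With a true linear gradient, a two-degree-of-freedom interaction test has about 43%, 79% and 96% power for the three gaps, against 53%, 86% and 98% for the linear test.

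**The case against.** The strongest reply is that the analysis is labelled exploratory and descriptive, the heterogeneity test is optional, and nothing stops the SAP from adding an interaction on the numeric scale. That stands, and it sets the importance: the point concerns the form of a test that may not be run. It does not remove the point, because the protocol itself names a two-level form, and a SAP that follows it inherits the loss.

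The advantage of the numeric score also depends on the effect changing gradually. With a step at the cut the ranking reverses, and a flexible form gives back part of the gain. This stands as a real cost.

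A reader might infer more than the protocol supports:
- *That the cut could be chosen after seeing unblinded results.* Section 14.1 puts a full SAP in place before any comparative analysis and has all analyses predefined there. The missing measure and cut value are ordinary SAP content.
- *That the factor is a 0-100 score.* No instrument is named. That range fits a KOOS domain but not the Oxford Knee Score, timed up and go or range of movement.
- *That the protocol contradicts itself by using fractional polynomials elsewhere.* Those are for covariate adjustment by age and BMI, not for effect modification. They show that the method is available to the analysts and no more.

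**Conclusion.** The point holds as a cheap improvement of low importance. The protocol plans a two-group form for a numeric effect modifier without giving a reason, and if a heterogeneity test is run on those groups it will usually be weaker than it need be. The loss is about 36% of the information for a median cut of a roughly normal score with a linear gradient, and about 25% to 53% over the other shapes and cuts tried, none more uneven than 20/80. Under the same linear assumption the numeric score adds 8 to 18 percentage points of power over a median split for gaps of 8 to 16 points.

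These figures are conditional on the stated cut, shape and gradient, so no single loss should be quoted as a fact about this trial. The sample size, the primary non-inferiority analysis and its conclusion are untouched.

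**What to change.** Amend the exploratory paragraph of section 14.1, or settle it in the SAP, along these lines: if heterogeneity by baseline functioning is tested, the test is a treatment-by-baseline-function interaction with the pre-randomisation score on its numeric scale. The SAP names the measure and the functional form in advance, linear by default. The result is reported as the estimated KJD-KR difference across the baseline range with a 95% confidence interval. The poor/better groups remain for descriptive display only.

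The cost is one sentence and one more model on data already collected. The price is an assumed form: a linear test is weaker if the effect steps at a threshold, and a more flexible form spends degrees of freedom. Choosing the form from the trial data would also need control of the type I error, which is why it should be fixed beforehand.
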